5.1 Method of Assigning Subjects to Treatment Groups

Subjects will be randomly assigned in a 1:1:1:1 ratio to receive SKI-O-703 100 mg BID, 200 mg BID, 400 mg BID, or matching placebo. An interactive voice or web response system (IxRS) will be used to administer the randomization schedule. The randomization schedule will be generated using SAS software version 9.3 or later (SAS Institute Inc., Cary, North Carolina) for IxRS, which will link sequential subject randomization numbers to treatment codes. The randomization schedule will be stratified by prior anti-TNF α biologic agents use (Yes or No), the number of previous csDMARDs treatments (0~2 or ≥ 3), specific geographic region (APAC, EMEA, and NA), and PK/PD sampling (Yes or No). It will also use an appropriate block size, which will not be revealed.

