6.2. Baseline Disease Characteristics

Variables indicated below will be summarized descriptively:

- Number of previous csDMARDs treatment
- Previous csDMARDs treatment category (0-2, \geq 3)
- Number of previous anti-TNF biologic agents use
- Previous anti-TNF biologic agents use (Yes, No)
- Baseline DAS28-hsCRP (based on 3 individual components including TJC, SJC and hsCRP)
- Baseline tender joint count based on 28 joints (TJC28)
- Baseline swollen joint count based on 28 joints (SJC28)
- Baseline HAQ-DI total score
- Baseline physician global assessment of disease activity (VAS)
- Baseline subject global assessment of disease activity (VAS)
- Baseline subject assessment of arthritis pain (VAS)

- Baseline hsCRP (mg/L)

The number of previous csDMARDs treatment is calculated as the number of unique medications that were captured in the eCRF page Prior and Ongoing RA Treatments and limited to the following standardized medication list: Methotrexate, Sulfasalazine, Hydroxychloroquine, Minocycline, Leflunomide, Hydroxychloroquine sulfate, Methotrexate sodium.

The number of previous anti-TNF biologic agents is calculated as the number of unique medications that were captured in the eCRF page Prior and Ongoing RA Treatments and limited to the following standardized medication list: Adalimumab, Etanercept, Infliximab, Certolizumab Pegol, Golimumab.

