7.2. Prior and Ongoing RA Medications

Medications reported on the Prior and Ongoing RA Treatments CRF page will be coded using the WHODD Enhanced B3 March 2018 version and grouped into relevant categories based on the ATC coding scheme.

Frequency table will be provided by treatment group and in total for prior and Ongoing RA medications using the Safety set. The number and percentage of subjects with prior and ongoing RA medications will be presented for each ATC level 2 term and generic drug names.

All the prior and ongoing RA medications will be listed.

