8.5. Subgroup Analysis

The focus of subgroup analysis will be limited to the baseline characteristics as listed below and the subgroup analysis will be conducted based on the ITT set for all the secondary efficacy endpoints specified in [Section 3.2.2](#). For VAS-related secondary endpoints (ACR responses and individual VAS assessments), the subgroup analysis will be restricted to subjects who completed the corresponding related VAS assessment consistently, same approach as described in the [Section 8.3.1](#) to identify the subjects to be included in the analyses.

- Number of previous csDMARDs treatments (0–2 csDMARDs, ≥ 3 csDMARDs)
- Previous anti-TNF α biologic agents use (Yes or No)
- Specific geographic region (APAC, EMEA, NA)

For ACR response endpoints, the number and percentage of responder and 95% Wald CIs will be provided by visit for each subgroup. The p-value of treatment comparison will be estimated by Chi-square tests within each subgroup. If all the subjects within a subgroup are responders or non-responders at a visit, only frequency counts and percentages will be provided for that subgroup and visit.

For other efficacy endpoints, the descriptive statistics of baseline, absolute value and change from baseline will be summarized by treatment group, scheduled visit and subgroup. By using the MMRM analysis as described in [Section 8.3.1](#), for each subgroup, the inferential statistics for treatment effect estimation and treatment comparisons will be provided by visit. In addition, subgroup comparison within treatment group will be provided as well by using a MMRM

analysis, which will be fitted with treatment group, subgroup, visit, treatment by visit interaction, treatment by subgroup interaction and baseline as fixed effects, and visit within subject as a repeated effect.

If too few subjects fall in the subgroup, the analysis within the subgroup may not be performed and only descriptive summary will be presented.

9. Safety Analysis

All the Safety analyses will be based on the Safety set.

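### SAP 6.2 counts previous csDMARDs over seven names that stand for five drugs, with no step merging salts, so a two-drug subject can be counted as having 3 or more

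*SAP*

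**What the plan says.** SAP 6.2 gives the SAP's only definition of the count: "The number of previous csDMARDs treatment is calculated as the number of unique medications that were captured in the eCRF page" that holds earlier and current RA therapy. A closed list then restricts which records qualify: "limited to the following standardized medication list: Methotrexate, Sulfasalazine, Hydroxychloroquine, Minocycline, Leflunomide, Hydroxychloroquine sulfate, Methotrexate sodium". The result is summarized as a number and as a two-level category, "Previous csDMARDs treatment category (0-2" against 3 or more.

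The next paragraph of SAP 6.2 uses the same wording for anti-TNF agents, "limited to the following standardized medication list: Adalimumab, Etanercept, Infliximab, Certolizumab Pegol, Golimumab". There, each of the five names is a different drug.

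Protocol 4.1.1, inclusion criterion 4b, recognises five csDMARDs and names no salt forms: methotrexate, sulfasalazine, hydroxychloroquine, minocycline and leflunomide. SAP 7.2 says that records from the same eCRF page are "coded using the WHODD Enhanced B3 March 2018 version and grouped into relevant categories based on the ATC coding scheme", and that the frequency table is presented by ATC level 2 term and generic drug name. It says nothing about merging salts for the count in 6.2.

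The same factor and cut-point appear elsewhere:
- Protocol 5.1 and SAP 4.4 use it as a randomization stratum, "the number of previous csDMARDs treatments (0~2 or ≥ 3", administered through the IxRS.
- SAP 8.5 uses it as a subgroup, "Number of previous csDMARDs treatments".
- SAP 8.2.3 includes it among the stratification factors in the imputation model.

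**The concern.** Counting unique entries works when each name on the list is a different drug, as in the anti-TNF list. It fails when two names denote one drug. A programmer who counts distinct standardized names gives a count of 2 to a subject whose methotrexate was recorded once as methotrexate and once as methotrexate sodium. With one other csDMARD that subject counts as 3 and crosses the cut-point.

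Against a count of actual drugs the error can only run upward, because a duplicate name can add to the count but never lower it. Any misplaced subject is therefore a less-treated subject in the more-treated category. If the subgroup analysis uses the derived category, that would blur the comparison between the two levels. It could also put a subject in a different level from the stratum entered at randomization, and the SAP has no rule to detect or list such differences.

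**Working it through.** The plan states no figure to reproduce here, so the check is to run the counting rule both ways.

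**Inputs.** The seven names and the cut-point (0-2 against ≥3) come from SAP 6.2. The five distinct drugs come from Protocol 4.1.1, criterion 4b. The pairing of base and salt is read from the names themselves.

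**Enumeration.** Take every subset of the seven names. Count the names as written, then count the distinct drugs with salts merged, and compare the categories.

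1. One-drug subjects: methotrexate alone or hydroxychloroquine alone can count as 1 or 2, and the other three drugs always count as 1. None reaches 3, so the category is right even where the number is not.
2. Two-drug subjects: there are 5 × 4 / 2 = 10 pairs. Three contain neither methotrexate nor hydroxychloroquine (sulfasalazine, minocycline and leflunomide taken two at a time) and always count as 2. The other 10 − 3 = 7 can count as 3 or more. Methotrexate plus hydroxychloroquine can count as 2, 3 or 4.
3. Name combinations with at most two real drugs and a count of 3 or more: methotrexate under both names with sulfasalazine, minocycline or leflunomide gives 3. Hydroxychloroquine under both names with the same three gives 3. Methotrexate with hydroxychloroquine gives 5 (four with three names, one with all four). The total is 3 + 3 + 5 = 11.
4. Subjects with three or more drugs are in ≥3 under either count. The maximum count is 7 instead of 5, but this does not change their category.

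With salts merged, none of the 11 combinations remains.

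**Illustration of size (assumed inputs).** Suppose 20% of subjects truly had three or more csDMARDs. Suppose a fraction m of the other 80% had two drugs with a duplicate name. The misplaced share of the ≥3 category is 0.8m / (0.2 + 0.8m):

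| m | Share misplaced |
|---|---|
| 0 | 0 |
| 0.5% | 0.004/0.204 = 2% |
| 1% | 0.008/0.208 = 4% |
| 5% | 0.04/0.24 = 17% |
| 15% | 0.12/0.32 = 37.5% |

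Neither the 20% nor any value of m is in the documents. The table shows only how the share depends on m.

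**Where the count is used.**
- Baseline table (SAP 6.2): uses the derived count directly. SAP 6 presents no inferential statistics on it.
- Subgroups (SAP 8.5): cover the secondary efficacy endpoints, which include change in DAS28-hsCRP. The section calls its factors baseline characteristics, which points to the 6.2 derivation, but it does not name the source.
- Imputation (SAP 8.2.3, reused under MAR in 8.2.4): calls the factor a stratification factor, which points to the IxRS, but again does not name the source.
- Primary ANCOVA (SAP 8.2.1): contains treatment and baseline DAS28-hsCRP only.

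**The case against.** The strongest reply is that the seven-name list is a capture filter. Both forms must be on it, or records coded to the salt would be lost even if counting is by ingredient. On that reading, unique medications already means unique drugs, and the generic drug names in SAP 7.2 fit that intention. This is a fair reading, and no passage says outright that salts score separately. But no passage says that they are merged either, and a literal implementation gives the wrong count. What stands of the objection is that the defect is a missing rule, not a declared decision to count salts as different drugs.

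It also stands that an error needs the same subject to have the same drug recorded under both names. A consistently coded subject is counted correctly. One drug may have several records, since the eCRF page holds prior and ongoing treatments. Protocol 5.8.1 requires an unchanged csDMARD route for the 4 weeks before Day 1, which leaves earlier changes possible. Whether any of this yields two coded names in one subject is not stated.

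A reader might infer that the randomization strata are wrong. The documents do not support this: strata are assigned through the IxRS, and nothing says that the IxRS uses the SAP derivation. A reader might also infer that a sizeable part of the ≥3 category is misplaced, which would require assuming a frequency that the documents do not give. Nor does the variable define a refractory group. It counts previous treatments on a form, with no requirement that they failed.

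**Conclusion.** The point holds as a gap in a derivation. As written, SAP 6.2 can place a two-drug subject in the ≥3 category, and 7 of the 10 two-drug pairs are open to this. The number of subjects affected is unknown and may be zero.

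The baseline table is exposed in any case: its numeric summary for any subject with a drug recorded under both names, its category only for two-drug subjects. The 8.5 subgroup analyses and the 8.2.3 imputation model are exposed only if they use the eCRF-derived count, which the SAP leaves open. Randomization and the primary ANCOVA are not affected. The conclusion rests on the literal reading of the rule. If ingredient-level counting was intended, the count is right in intent and the SAP only needs to say so.

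**What to change.** In SAP 6.2, state that Methotrexate sodium is mapped to Methotrexate and Hydroxychloroquine sulfate to Hydroxychloroquine before unique medications are counted, so that the count runs from 0 to 5. Keep all seven names on the list so that no record is lost.

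In SAP 8.5 and 8.2.3, state whether the csDMARD factor is the IxRS stratum or the category derived in 6.2. Add a listing of subjects for whom the two differ.

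The cost is a few sentences in the SAP, a two-line mapping and one listing, all before database lock. If counting by ingredient was already intended, no result changes.

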6.3. Alcohol, Tobacco and Drug Usage

The following characteristics will be summarized:

- Smoking history (never a smoker or user of chewing tobacco or vaping devices, prior smoker or user, current smoker or user)
- Alcohol history (never a drinker, prior drinker, current drinker)

6.4. Medical History

Medical history will be coded according to the Medical Drug Regulatory Activities (MedDRA) version 21.0 or higher. The number and percentage of subjects who experience any medical history will be presented by treatment group and overall for each system organ class (SOC) and preferred term (PT), with SOCs and PTs within each SOC presented in a descending order of overall subject incidence (then the frequency within treatment groups from high dose to low dose and placebo group, if applicable).

7. Treatments and Medications

7.1. Prior and Concomitant Medications

Medications reported on the Prior and Concomitant Medications CRF will be coded using the World Health Organization Drug Dictionary (WHODD) Enhanced B3 March 2018 version and grouped into relevant categories based on the Anatomical Therapeutic Chemical (ATC) coding scheme.

A prior medication will be any medication stopped prior to the first dose of study drug.

A concomitant medication will be any medication that is either initiated before the first dose of study drug, or initiated on/after the date of the first dose of study drug, and continued during the study treatment period.

Frequency table will be provided by treatment group and overall for prior medications based on the Safety set. The number and percentage of subjects who have prior will be presented by treatment group and overall for each therapeutic drug class (ATC level 2) and generic drug names, with therapeutic drug class and generic drug name within each therapeutic drug class in a decreasing order of overall frequency (then the frequency within treatment groups from high dose to low dose and placebo, if applicable). Similar frequency tables will be provided by treatment group for permitted and prohibited concomitant medications based on the Safety set.

The list of prohibited concomitant medications should be reviewed and finalized by sponsor designee prior to the final database lock.

A listing of prior and concomitant medications by subject will be provided, with an indicator to identify the prior and concomitant medications.

7.2. Prior and Ongoing RA Medications

Medications reported on the Prior and Ongoing RA Treatments CRF page will be coded using the WHODD Enhanced B3 March 2018 version and grouped into relevant categories based on the ATC coding scheme.

Frequency table will be provided by treatment group and in total for prior and Ongoing RA medications using the Safety set. The number and percentage of subjects with prior and ongoing RA medications will be presented for each ATC level 2 term and generic drug names.

All the prior and ongoing RA medications will be listed.

7.3. Study Treatments

7.3.1. Extent of Exposure

Treatment duration and total dose will be summarized by treatment group based on the Safety set.

Treatment duration (in days) is calculated as the date of last dose of study drug – the date of the first dose of study drug + 1. Summary statistics of treatment duration, as well as frequency

summary of treatment duration categories (e.g. <2 weeks, ≥ 2 to <4 weeks, ≥ 4 to <8 weeks, ≥ 8 weeks) will be provided.

Total dose is defined as the total number of capsules taken over the treatment period, which is calculated as total number of capsules dispensed minus the total number of capsules returned. Summary statistics of total dose will be provided.

7.3.2. Treatment Compliance

Treatment compliance (%) will be calculated for each subject as 100 times total dose divided by the intended total dose that should be taken over the treatment period. The intended total dose is calculated as 8 times the treatment duration. Compliance will be summarized using descriptive statistics by treatment group. The acceptable range for compliance is defined as between 80% - 120%. The number and percentage of subjects will be summarized by category $< 80\%$, $\geq 80\%$ to $\leq 120\%$, and $> 120\%$.

A subject data listing of study drug accountability will be provided, with the capsules dispensed, capsules returned, capsules taken, intended total dose and treatment compliance presented.

8. Efficacy Analysis

The primary analyses of all efficacy endpoints will be based on the ITT set, and then repeated using the PP set. The analyses of primary endpoint and secondary efficacy endpoints ACR20, ACR50 and ACR70 will also be provided based on the mITT set.

Each efficacy endpoint will be descriptively summarized by treatment group over time. In the summary for a post-baseline time point, subjects who have both values at baseline and at the time point will be included. Listings of all the efficacy endpoints will be provided by subjects.

Statistical comparisons will be performed between each of active treatment groups and the placebo group. All the statistical tests will be 2-sided and performed at a significance level of 0.05, leading to 95% CIs (2-sided). There will be no adjustment for multiplicity.

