3.1.1 Dose Interruption and Reduction

Adverse Events:

It is recognized that some AEs may require dose adjustment or study drug discontinuation. Guidelines for dose reduction are outlined in Table 3-1.

Table 3-1 Guidelines for Dose Interruption and Reduction^a

AE	Occurrence ^b	Action
ALT or AST elevations (range 3 to 5 \times ULN) or ALP $>3 \times$ ULN and $>2 \times$ baseline	First	
 • If asymptomatic (no nausea, anorexia, vomiting), repeat test within 72 hours^c and, if stable or lower, may continue dosing of study drug. • If on repeat test value has increased further but remains $<5 \times$ ULN and asymptomatic, withhold study drug and retest weekly until values becomes stable. When stabilized to $<5 \times$ ULN, continue dosing with the study drug. • If symptomatic or $>5 \times$ ULN, withhold csDMARDs and study drug. Follow the subject weekly until symptoms abate and values return to baseline per confirmation from central laboratory, at which time csDMARDs may be restarted at the prior dose and study drug may be restarted at a reduced dose by skipping one of the doses. 
Note: Discontinue study drug permanently if the ALT elevation is accompanied by an elevation in direct bilirubin to >2 mg/dL (34.2 mmol/L).

	Second	Discontinue study drug permanently.
ANC $<1500/\text{mm}^3$ or $<1.50 \times 10^9/\text{L}$	First	Study drug must be withheld. Repeat the test weekly until value return to baseline or $\geq 1500/\text{mm}^3$ or $\geq 1.5 \times 10^9/\text{L}$, and then restart at a reduced dose by skipping one of the doses.
	Second	Discontinue study drug permanently if the intolerance reoccurs or persists.
Sustained increased systolic (>170 mm Hg) or sustained increased diastolic (>100 mm Hg) blood pressure in a previously normotensive subject	First	
Study drug may be withheld and then restarted at a reduced dose by skipping one of the doses.
 
Irrespective of study drug dose adjustment, subjects who develop a sustained increased systolic (>140 mm Hg) or a sustained increased diastolic (>90 mm Hg) blood pressure should be started on antihypertensive medications (ie, diuretics, calcium channel blockers, ACE inhibitors, etc.) or have their antihypertensive regimen adjusted if already on any antihypertensive agent.

	Second	Discontinue study drug permanently if the hypertension reoccurs or persists.

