5.2 Treatments Administered

Subject specific doses will be prepared and checked by blinded pharmacy staff and administered by appropriately trained blinded clinic staff as delegated by the principal investigator (PI) at the study site. The study drugs will be similar in number and appearance for each cohort to maintain the study blind. The following dosing scheme will be performed:

Cohort	Treatment Arm	Treatment per Dosing Timepoint	
		Placebo Capsule	SKI-O-703 100 mg Capsule
1	Placebo	4	-
2	SKI-O-703 100 mg	3	1
3	SKI-O-703 200 mg	2	2
4	SKI-O-703 400 mg	-	4

SKI-O-703 100 mg BID, 200 mg BID, 400 mg BID, and placebo will be administered orally. The study medication will be taken no later than 30 minutes after food.

Day 1 Dosing:

On Day 1, subject will be administered his/her first dose of study medication no later than 30 minutes after food with approximately 8 ounces (240 mL) of water by the study site personnel. The study site personnel will check the subject's mouth to ensure the study drug and entire volume of water was swallowed.

The second dose will be administered approximately 12 hours (± 2 hours) after the first dose. The second dose and subsequent doses will be self-administered by the subject. The subjects will be instructed to take study medication no later than 30 minutes after food.

Study Visit Day Dosing:

On study visit days, subjects will take the first dose of study drug no later than 30 minutes after food in the office under the guidance of study site personnel after all specified study tests and procedures have been completed, and new bottles of medication have been issued. However, if the visit cannot be scheduled within the regular dosing schedule for the first daily dose of a new cycle, the subject will be instructed to take the first dose at the regular schedule on that visit day from the bottle of the preceding cycle.

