4.5. Analysis Sets

The following analysis sets will be used:

Safety set: The Safety set is defined as all subjects who receive at least one dose of study drug (SKI-O-703 or placebo). Subjects will be analyzed as treated. This population will be used for summaries of safety data.

Intent-to-Treat (ITT) set: The ITT set is defined as all randomized subjects who receive at least one dose of study drug (SKI-O-703 or placebo). Subjects will be analyzed as randomized. This population will be used for all efficacy analyses and summaries of demographics and baseline characteristics data.

Modified Intention-to-Treat (mITT) set: The mITT set is defined as all the subjects who receive at least one dose of study drug (SKI-O-703 or placebo) and have at least 1 postbaseline assessment. Subjects will be analyzed as randomized. This population will be used for efficacy summaries and will include imputed data for subjects who withdraw from the study prior to the Week 12 visit.

Per Protocol (PP) set: The PP set is defined as all the subjects in ITT set who don't have any major protocol deviation(s) which will be flagged in the protocol deviation list and be compliant with the treatment as defined in [Section 7.2.2](#). All the efficacy analyses will be repeated on PP set. Subjects will be analyzed as randomized.

Pharmacokinetic (PK) set: The PK set will consist of all subjects who receive SKI-O-703 and have at least 1 measurable plasma concentration. Subjects who have partial data and/or major protocol deviations that may impact PK, and subjects who experience emesis, will be evaluated on a case-by-case basis and may be excluded from the PK population. This population will be used for summaries of PK data.

Pharmacodynamic (PD) set: The PD set will consist of all subjects who receive at least 1 dose of study drug (SKI-O-703 or placebo) and have at least 1 evaluable postdose PD value. Subjects who have partial data and/or major protocol deviations that may impact PD will be evaluated on a case by case basis and may be excluded from the PD population. This population will be used for summaries of PD data

Pharmacokinetic (PK)/pharmacodynamic (PD) set: The PK/PD set will consist of all subjects included in both the PK and PD populations. This population will be used for the PK/PD analyses.

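### Compliance is scored against 8 capsules a day for every subject, so a subject who follows a directed dose reduction or interruption may fall below 80% and leave the per-protocol set

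*SAP*

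**What the plan says.** SAP Section 7.3.2 defines the score: "Treatment compliance (%) will be calculated for each subject as 100 times total dose divided by the intended total dose" due over the treatment period. It then fixes the denominator: "The intended total dose is calculated as 8 times the treatment duration". The acceptable range is 80% to 120%.

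SAP Section 7.3.1 supplies the other two terms. Total dose is "calculated as total number of capsules dispensed minus the total number of capsules returned". Duration is set by the first and last doses: "Treatment duration (in days) is calculated as the date of last dose of study drug" minus the date of the first dose, plus one day. Days off drug between those two dates therefore count as treatment days.

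Protocol Table 3-1 (Section 3.1.1) provides for withholding and for reduced dosing after certain adverse events. In the neutrophil row the drug is withheld until recovery, "then restart at a reduced dose by skipping one of the doses". A confirmed QTcF above the stated threshold leads to an interruption of at most 14 days. A clinically significant QTcF rise of more than 30 ms leads to a one-dose reduction that lasts to the end of the study. The blood-pressure and nausea rows leave withholding to discretion.

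SAP Section 4.5 limits the PP set to ITT subjects who have no major deviation and who also "be compliant with the treatment as defined in" Section 7.2.2. The SAP has no such section; 7.2 covers RA medications and has no subsections. Protocol Section 7.5 defines the PP set by the absence of important deviations and sets no compliance condition. SAP Section 14 reports no changes to the planned analysis.

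**The concern.** The SAP describes its denominator as the dose that ought to have been taken. For a subject on a directed reduction that is 4 capsules a day, and during a directed interruption it is none. The formula keeps counting 8. It can therefore label a subject non-compliant for doing what the protocol told them to do.

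All efficacy analyses are repeated on the PP set, so the label has a consequence there. The subjects at risk are those with the adverse events listed in Table 3-1, so the exclusion is driven by tolerability and not by carelessness with dosing. If those events differ by arm, the PP comparison would lose subjects unevenly. With about 37 subjects per arm, each exclusion removes 1/37 = 2.7% of an arm.

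**Working it through.** **The plan's own figure.** The dosing table in Protocol Section 5.2, headed "Treatment per Dosing Timepoint", gives 4 capsules in every arm (4+0, 3+1, 2+2 or 0+4 placebo plus active). Twice daily makes 4 × 2 = 8 a day, and 8 × 84 = 672 over the planned 84 days. The figure of 8 is right for full dosing.

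**Score of a fully adherent subject.** Let D be treatment duration, i the days off drug between first and last dose, and r the days on one dose. Assume that every directed capsule is taken and every other capsule is returned.

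- Taken: 8(D − i − r) + 4r
- Intended under the SAP: 8D
- Compliance: 100 × [1 − (i + r/2)/D]

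The score is below 80% exactly when i + r/2 > 0.2D. At D = 84 the threshold is 16.8 days.

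**Results at D = 84**

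| Directed course | i | r | i + r/2 | Score | Meets 80%? |
|---|---|---|---|---|---|
| Reduced Day 15 to 84 | 0 | 70 | 35 | 58.3% | no |
| Reduced Day 29 to 84 | 0 | 56 | 28 | 66.7% | no |
| Reduced Day 43 to 84 | 0 | 42 | 21 | 75.0% | no |
| Reduced Day 51 to 84 | 0 | 34 | 17 | 79.8% | no |
| Reduced Day 52 to 84 | 0 | 33 | 16.5 | 80.4% | yes |
| Reduced Day 57 to 84 | 0 | 28 | 14 | 83.3% | yes |
| 14 days off, full-dose restart | 14 | 0 | 14 | 83.3% | yes |
| 16 days off, full-dose restart | 16 | 0 | 16 | 81.0% | yes |
| 17 days off, full-dose restart | 17 | 0 | 17 | 79.8% | no |
| 7 days off, then 20 reduced | 7 | 20 | 17 | 79.8% | no |
| 14 days off, then 6 reduced | 14 | 6 | 17 | 79.8% | no |
| 14 days off from Day 15, then reduced to Day 84 | 14 | 56 | 42 | 50.0% | no |
| 14 days off from Day 57, then reduced to Day 84 | 14 | 14 | 21 | 75.0% | no |

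The tolerance shrinks with D: 14 days off alone fails once 14 > 0.2D, that is, when D is below 70.

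**A contrast.** A subject who takes every capsule and stops for good on Day 14 has D = 14 and i = r = 0, and scores 100%. A subject who stays on drug to Day 84 with a directed reduction from Day 15 scores 58.3%.

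**With a directed-dose denominator.** For a reduction from Day 15 to Day 84 the intended total is 8 × 14 + 4 × 70 = 392. From Day 29 it is 8 × 28 + 4 × 56 = 448, and from Day 57 it is 8 × 56 + 4 × 28 = 560. The adherent subject took exactly that number, so each score is 100%.

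**The case against.** The best defence is that the rule is a minimum-exposure condition: in a dose-ranging trial the PP set may reasonably be kept to subjects who took at least 80% of the assigned regimen. Under a directed-dose denominator, a 400 mg BID subject halved from Day 15 takes 392 of 672 capsules, counts as fully compliant and is still analysed as 400 mg BID. That loss of dose separation is a real cost. But the formula does not impose minimum exposure either, because duration ends at the last dose: the subject who stops on Day 14 passes. As written it measures neither exposure nor adherence.

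Other objections stand and limit the point:

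- A reader might infer that every subject with a directed modification is excluded. The table above shows otherwise. The only interruption with a stated length, 14 days, passes by itself over 84 days, and drug that is never restarted is not penalised.
- Only the QTcF-rise row says that the reduction lasts to the end of the study. The other rows give no length, so running those reductions to Day 84 is illustrative.
- A reader might infer that PP would compare selected tolerators on active drug with a nearly complete placebo arm. The documents give no modification rates by arm. The healthy-volunteer studies in Protocol Section 1.1 show no excess of treatment-emergent events on drug (19.4% against 25.0% on placebo, and 27.8% against 33.3%). They are too small and short to rule out an imbalance, and they do not support asserting one.
- Exclusion from PP depends on reading the reference to Section 7.2.2 as 7.3.2. That is the only compliance definition in the SAP, so the reading is likely, but it remains an inference.

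**Conclusion.** The compliance definition is wrong as written, and it affects a supportive analysis only. A fully adherent subject may be scored non-compliant when interruption days plus half the reduced days exceed 20% of treatment duration. At 84 days that covers reductions of 34 days or more, interruptions of 17 days or more, and many interruptions followed by reduced dosing. Reductions of 33 days or less, and interruptions of 16 days or less with a full-dose restart, still pass.

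On the likely reading of the cross-reference, subjects who fail are dropped from the SAP's PP set although they followed the protocol, and the protocol's own PP definition would not drop them for compliance. Because the exclusion follows adverse events, it could plausibly differ by arm. Neither that difference nor the number of subjects affected can be calculated from the documents. A reader might also infer that the main result is at risk; it is not, because the primary analysis uses the ITT set, which has no compliance condition.

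**What to change.** Before database lock:

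- In SAP 7.3.2, define the intended total dose as the capsules directed under the protocol in each period: 8 a day at full dosing, 4 a day during a directed one-dose reduction and 0 during a directed interruption. State whether modifications that Table 3-1 leaves to the investigator's discretion count as directed.
- Report the present ratio separately, as dose intensity, with the exposure summaries.
- Correct the Section 7.2.2 reference in SAP 4.5.
- Reconcile the SAP and protocol PP definitions, and record any remaining difference in SAP Section 14.

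The text changes are short. The work lies in the data: start and stop dates of directed modifications must come from the dosing diary, source documents or eCRF. The documents do not show that these dates are in the analysis database, so the sponsor should confirm that they are available. The PP set will then include some subjects on a reduced dose, and the dose-intensity summary will show how much they took. No dosing rule changes.
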